8.2 Secondary Variables

Analyses of the secondary endpoints will be based on the grades shown in ICDRG table in Section 8.1.

For Treatment Regimen 1 and 2, proportion of subjects that have a ≥ 1 grade reduction of the cutaneous reaction to nickel sulfate in at least one patch region after treatment.

For Treatment Regimen 2, proportion of subjects that have a ≥ 1 grade reduction of the cutaneous reaction to nickel sulfate in at least one patch region at 48 hours (Day 3) will be assessed.

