#### Nickel Sulfate and Vehicle Control Patches

Follow the instructions in [Appendix C](#). Follow the manufacturer's instructions for filling the unit chambers. Concentrations of 1%, 2.5% and 5% nickel sulfate solution will be used to determine the subject's allergic reaction to nickel. Apply the test patches to a clean surface on the upper back (at least 2 cm above the area to be used for the post-screening visits). Have the subject return to the study site after 48 hours to have the test results interpreted.

The concentration of nickel sulfate that causes no greater than + + cutaneous reaction (International Contact Dermatitis Research Group [ICDRG] scoring scale, see [Appendix B](#)) will be the assigned dose for use per subject for the study. One half (50%) of study subjects will

be treated using the nickel concentration that elicits a + cutaneous reaction and the other half (50%) of study subjects will be treated with the nickel concentration that elicits a ++ cutaneous reaction. Any subjects not meeting the cutaneous reaction scale will be a screen failure.

Record the nickel sulfate concentration to be used for the subject in the subject's source documentation.

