### Dataset for Analysis

The primary analysis data set for this study will consist of all evaluable subjects. An evaluable subject is one who has completed dosing (or prematurely discontinued the administration due to a toxicity) and has undergone sufficient assessments to allow an assessment of the tolerability of the administration. A secondary analysis data set will consist of all intent-to treat subjects (ITT) (i.e., all subjects enrolled, defined as subjects assigned a subject identification number at the time of study enrollment in anticipation of receiving a dose of study drug). The safety analysis data set is all subjects exposed to rHuPH20 or placebo control.

The hypothesis is that 1) pre-treatment of rHuPH20 prior to nickel allergy testing will decrease the severity of the allergic skin reaction as compared to placebo control and 2) rHuPH20 will decrease the severity of nickel contact dermatitis as compared to control. The null hypothesis for this study is that rHuPH20 will not be different than what will be observed from placebo control. The alternative hypothesis is that rHuPH20 will be better than placebo control.

The sample size of 20 evaluable subjects is intended to provide a sufficient sample size to allow for a meaningful comparison between rHuPH20 and placebo control.

All data collected, including demographics, baseline information, contact dermatitis scoring, safety data, will be summarized by treatment group. Descriptive statistics including the number of observations (N), mean, standard deviation, median, and range will be presented for the continuous variables. Frequency and percentage will be presented for categorical variables. Figures of the individual measurements over time by subject and means by treatment group may also be provided.

Descriptive statistics will be used to summarize all efficacy variables. No formal statistical comparisons between treatments are planned.

All safety data will be examined, including AEs, physical examination findings, and vital signs. The incidence of subjects with AEs will be tabulated by MedDRA System Organ Class (SOC) and Preferred Term, seriousness, severity grade, relatedness to study drug, and localization to infusion site. Descriptive statistics will be used to summarize all safety variables.

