cutaneous reaction an ID syringe push bolus injection of either rHuPH20 or placebo control. Each injection will be administered once daily for 5 days. Prior to each daily injection, subjects will be evaluated for efficacy, safety, and tolerability. A final evaluation will be conducted 7 days after the last dose of study treatment.

Treatment Regimen 2 (TR2-5 – TR2-8):

This regimen will assess the prevention and treatment of contact allergy to nickel sulfate. Each subject will receive in the center of each lower space on the back, either an ID syringe push bolus injection of rHuPH20 or placebo control. Exactly 10 minutes after the injection, a single row of four patches (1, 2.5, or 5% nickel sulfate patches; determined for each subject during the Screening period) will be placed over the center of the ID injection. After 48 hours, the patches will be removed and an assessment will be made of the reaction site as per the ICDRG scoring system. The subject will receive an ID injection of the same study drug from pre-treatment in the center of the cutaneous reaction once daily for 5 days. Subjects will be evaluated for efficacy, safety, and tolerability, on a daily basis. A final evaluation will be conducted 7 days after the last dose of study treatment.

For a given subject, the anticipated duration of time on study is up to 35 days, which include Visit 1 (screening, within 21 days prior to receiving study drug), Visit 2 (Day 1), Visit 3 (Day 3), Visits 4 – 7 (Day 4 – 7) and Visit 8 (Day 14).

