8.1 Primary Variables

The primary efficacy endpoint will be based on the International Contact Dermatitis Research Group (ICDRG) Scoring Scale. Using the ICDRG Scoring Scale, each score will be assigned a Sponsor-defined “grade”. Scores with stronger reactions will be assigned grades with higher values with a maximum grade of 3; scores with weaker reactions will receive lower values with a minimum grade of 0. Grade assignments based on the ICDRG Scoring Scale are shown in the table below.

International Contact Dermatitis Research Group (ICDRG) Scoring Scale

Grade	Score	Interpretation
0	-	Negative reaction
1/2	?	Doubtful reaction; faint macular erythema only
1	+	Weak (nonvesicular) positive reaction; erythema, infiltration, papules, vesicles
2	++	Strong (vesicular) positive reaction; erythema, infiltration, papules, vesicles
3	+++	Extreme positive reaction; bullous reaction
NA	IR	Irritant reaction of different types

Treatment effect of rHuPH20 or placebo control injection on the exposure to topical nickel allergen will be assessed using ICDRG grades for Treatment Regimens 1 and 2 at Day 3 through Day 7 and Day 14.

Regimen 2 only: For each subject, the day of maximal ICDRG score will be determined for each injection type (rHuPH20 and Placebo). The maximal ICDRG score will be the highest score reported for each subject. If the maximal ICDRG score for a particular subject is reported more than one time, the first instance will be used to determine the day when the maximal ICDRG score was reached.

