8.4 Baseline Values

For analyses based on grades, each treatment region will be assigned its own baseline value. The baseline values for regions under Treatment Regimen 1 and 2 will be the values collected at Day 3.

The baseline values for TEWL measurements and Chromometer readings will be the assessments collected on Day 1.

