9. STUDY ANALYSIS

The hypothesis for this study is that 1) pre-treatment or rHuPH20 prior to nickel allergy testing will decrease the severity of the allergic skin reaction as compared to placebo control and 2) rHuPH20 will decrease the severity of nickel contact dermatitis as compared to control. The null hypothesis is that rHuPH20 will not be different than what will be observed from placebo control.

Figures, listings and descriptive statistics will be used to summarize all efficacy variables. No formal statistical comparisons between treatments are planned.

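### In Regimen 2 the after-treatment responder is measured from a Day 3 grade that the Day 1 injection may already have lowered, so successful prevention pulls the rHuPH20 proportion down

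*SAP*

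**What the plan says.** SAP 8.2 gives one responder definition for both regimens, assessed after treatment and met if any one site qualifies: "For Treatment Regimen 1 and 2, proportion of subjects that have a ≥ 1 grade reduction of the cutaneous reaction to nickel sulfate". SAP 8.4 supplies the reference: "The baseline values for regions under Treatment Regimen 1 and 2 will be the values collected at Day 3", with each site serving as its own baseline.

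The regimens differ in what has happened by Day 3. In Regimen 1 the patches come off, the reaction is graded and the first injection follows. In Regimen 2 (SAP 3) the site is injected with rHuPH20 or placebo on Day 1, and the patches go on afterwards: "Exactly 10 minutes after the injection, a single row of four patches" is placed over the injection. After the Day 3 reading, "The subject will receive an ID injection of the same study drug from pre-treatment in the center of the cutaneous reaction once daily for 5" treatment days.

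Hypothesis 1 in SAP 9 is that pre-treatment "prior to nickel allergy testing will decrease the severity of the allergic skin reaction as compared to placebo control"; Protocol Section 8 says the same. Hypothesis 2 is that rHuPH20 lessens the severity of the dermatitis itself.

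SAP 8.1 converts ICDRG scores to grades 0, 1/2, 1, 2 and 3: "scores with weaker reactions will receive lower values with a minimum grade of 0". Neither document has a rule for sites whose Day 3 grade is below 1.

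**The concern.** A baseline for change should be fixed before the randomised treatment can act. In Regimen 1 the Day 3 grade meets that condition. In Regimen 2 it does not: it is the first reading at which prevention could show, and it is also the starting point from which later success is counted.

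Combined with the floor of the scale, this works against the drug. A site on which the reaction was prevented has nothing left to lose and stays in the denominator as a non-responder. A placebo site that reacted to ++ can resolve and count as a success. At stake is the reading of the prevention arm of a proof-of-concept study, because SAP 9.1 names the responder proportion as one of two items for the medical review that feeds the clinical study report.

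**Working it through.** The plan states no response rates, effect size or power, so there is no figure to reproduce. The check has a part that follows from the scale alone and a part that illustrates size.

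**1. Which falls of at least 1 grade are possible (SAP 8.1 scale)**

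- From Day 3 grade 0: none.
- From 1/2: none; the largest possible fall is 1/2.
- From 1: only to 0; a fall to 1/2 does not count.
- From 2: to 1, 1/2 or 0.

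Any lowering of Day 3 grades from 2 or 1 therefore narrows or closes the route to response. This needs no assumption.

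**2. Illustration with equal resolution after Day 3**

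From the documents: two rHuPH20 and two placebo sites per subject in each regimen (Protocol 3.1); response means at least one site. At screening, "One half (50%) of study subjects will" be assigned the concentration that gave + and the other half the one that gave ++ (Protocol 5.1.1).

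Assumed: unprevented sites are half + and half ++ on Day 3; 40% of + and 70% of ++ sites later fall by at least 1 grade on either injection; prevention clears a fraction q of rHuPH20 sites by Day 3; the two sites are independent.

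- Placebo site rate: 0.5 × 0.40 + 0.5 × 0.70 = 0.55. At least one of two: 1 − 0.45² = 0.798.
- rHuPH20 site rate: (1 − q) × 0.55. At least one of two: 1 − [1 − (1 − q) × 0.55]².

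| q | rHuPH20 site rate | rHuPH20 responders | Placebo responders | Deficit |
|---|---|---|---|---|
| 0.25 | 0.4125 | 1 − 0.5875² = 65% | 80% | 14 points |
| 0.50 | 0.275 | 1 − 0.725² = 47% | 80% | 32 points |
| 0.75 | 0.1375 | 1 − 0.8625² = 26% | 80% | 54 points |

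The protocol splits subjects, not sites, between + and ++. Mixing at subject level gives placebo 0.5 × (1 − 0.6²) + 0.5 × (1 − 0.3²) = 77.5% and, at q = 0.50, rHuPH20 0.5 × (1 − 0.8²) + 0.5 × (1 − 0.65²) = 46.9%. The deficit is 31 points, little changed.

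**3. Illustration with faster resolution on rHuPH20**

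Assume rHuPH20 fall rates of 60% (+) and 90% (++), a site rate of 0.75; placebo as in step 2.

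- q = 0: 1 − 0.25² = 94% v 80%, an advantage of 14 points.
- q = 0.25: site rate 0.75 × 0.75 = 0.5625; 1 − 0.4375² = 81% v 80%.
- q = 0.50: site rate 0.375; 1 − 0.625² = 61% v 80%.

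Here preventing a quarter of reactions does not produce a deficit, but it erases almost all of the advantage that faster resolution alone would show.

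**4. A second model**

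Let each site drop one scale category per day with probability r, with no worsening after Day 3, half of subjects at + and half at ++. Take r = 0.3 for both injection types and four daily steps to Day 7. A + site needs two drops: 1 − 0.7⁴ − 4 × 0.3 × 0.7³ = 0.348. A ++ site needs one: 1 − 0.7⁴ = 0.760. Placebo responders are 0.5 × (1 − 0.652²) + 0.5 × (1 − 0.240²) = 76%. With full suppression of a fraction q, rHuPH20 responders fall from 76% (q = 0) to 47% (q = 0.5) and 0% (q = 1). If rHuPH20 doubles the daily probability (0.4 v 0.2), it scores 88% v 58% at q = 0, 57% v 58% at q = 0.5 and 0% at q = 1.

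In both models the rHuPH20 proportion falls as prevention rises; whether it drops below placebo depends on the effect after Day 3.

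**The case against.** Four points stand on the other side.

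First, a reader might infer that a working drug must score below placebo in Regimen 2. The documents do not support that. Regimen 2 sites receive five further daily injections and hypothesis 2 expects these to help; a deficit at every level of prevention follows only if that effect is assumed away. If prevention merely moves ++ to + and every site later clears to 0, the injection types tie.

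Second, a reader might infer that prevention would be reported as failure. That too goes beyond the text. The endpoint is secondary, no formal comparison is planned, and the proportion has no table of its own and is assessed by qualitative review. Figure 1 and Listing 8 show every site's grade with its injection type, including on Day 3, so low Day 3 grades on rHuPH20 would be visible. This lowers the severity. It does not make the stated rule sound, and the one ICDRG summary table does not correct it: Table 6 places a subject whose sites stayed clear in the same row as one whose sites stayed at ++, both being no worse than on Day 3.

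Third, SAP 8.2 does not say that the proportion is reported by injection type, nor which days count as after treatment. The by-type reading is inferred from the intra-subject comparison and by-type displays in SAP 9.1. Pooled over injection types, the proportion could show no drug effect at all. The later days are inferred from the SAP 2 objective listing Days 4 to 7 and 14.

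Fourth, Day 3 could be defended as isolating the effect of treatment given after patch removal. In Regimen 2 it cannot, because the randomised drug has already acted on the starting value and sites with no reaction left to treat are kept as failures.

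**Conclusion.** The concern holds in a conditional form. That a Regimen 2 site at grade 0 or 1/2 on Day 3 cannot respond follows from SAP 8.1, 8.2 and 8.4 without assumptions. That this pulls the rHuPH20 proportion down as prevention improves rests on reading the endpoint by injection type. The sizes rest on assumed fall rates and independent sites: about 14 to 54 points for 25% to 75% prevention with equal resolution after Day 3, and none (81% v 80%) with faster resolution on rHuPH20 and 25% prevention. The pull can mask or reverse a benefit; it does not ensure a loss. Regimen 1 is unaffected. Because the endpoint is descriptive and Day 3 grades remain on display, this is a should-fix point and not a critical one.

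**What to change.** In SAP 8.2 and 8.4, confine the Day 3-referenced after-treatment responder to Regimen 1. For Regimen 2, replace it with the same-day, within-subject comparison of ICDRG grade between rHuPH20 and placebo sites at Days 3 to 7 and Day 14, tabulated by injection type. One workable form, for each day, is the grade distribution by injection type plus the number of subjects whose mean rHuPH20 grade is lower than, equal to or higher than their mean placebo grade.

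Reduction from the subject's screening grade at the assigned concentration may be added as supportive only. Its limits should be stated: it comes from a single patch on another day and skin area, and it is likely to reach a ceiling by Day 14 (placebo 94% to 100% in the second model with r from 0.2 to 0.5).

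The same change to SAP 8.4 also addresses the Regimen 2 48-hour endpoint. As written, that endpoint is Day 3 minus Day 3 and so zero for every site; the Day 3 comparison between injection types takes its place.

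The cost is SAP wording, one derived variable and one table. All grades are already collected. Protocol 2.2 names neither a regimen nor a reference grade for the after-treatment item. The change should be made before the blind is broken, since SAP 4 treats later analyses as post hoc. What is given up is a single responder definition shared by both regimens.

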2. OBJECTIVES

The primary objectives of the study are:

- Determine the treatment effect of rHuPH20 or placebo control injection on the exposure to topical nickel allergen (Treatment Regimens 1 and 2)
- Determine the time to onset and severity of cutaneous reaction to nickel allergen after pre-treatment with rHuPH20 or placebo control (Treatment Regimen 2)
- Assess the safety and tolerability of the rHuPH20 injection

Secondary objectives include:

- Proportion (%) of subjects who, with pre-treatment, have a ≥ 1 grade reduction of the cutaneous reaction to nickel sulfate in at least one patch region at 48 hours
- Proportion (%) of subjects with a ≥ 1 grade reduction of the cutaneous reaction to nickel sulfate in at least one patch region after treatment
- Proportion (%) of subjects that have a ≥ 1 grade reduction of the cutaneous reaction to nickel sulfate in at least one patch region at Days 4, 5, 6, 7 and 14.
- Safety and tolerability of the injection based on AEs, physical examinations, and vital signs

Descriptive-Only parameters include:

- Chromometer readings of the allergen test sites on Day 1, Day 3 (48 hrs), Day 4 (72 hrs) and Day 5 (96 hrs) after the placement of the patches
- TEWL (Trans-epidermal water loss) assessment on Day 1, Day 3 (48 hrs), Day 4 (72 hrs) and Day 5 (96 hrs) after the placement of the patches

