9.1 Statistical Analyses

The primary analysis is the pair-wise intra-subject comparison of endpoint parameters for the injections with and without rHuPH20. The secondary analysis covers safety and other endpoint parameters (see Section 10).

ICDRG scores will be shown for Treatment Regimen 1 and Treatment Regimen 2 by injection types (rHuPH20 or Placebo) at Baseline, Day 4, Day 5, Day 6, Day 7 and Day 14. ICDRG scores will be reported by subject using figures (Figure 1) and listings (Listing 8).

A qualitative medical review of the ICDRG scores will be used to investigate:

- Possible treatment effect of rHuPH20 or placebo control injection on the exposure to topical nickel allergen.
- Proportion of subjects that have a ≥ 1 grade reduction in at least one patch region.

At the conclusion of the study, findings from the medical review will be summarized in the clinical study report.

For Treatment Regimen 2, the day of maximal ICDRG Score will be used to assess the possible effect each injection type has on the onset of reaction to topical nickel allergen. The day of maximal ICDRG Score will be summarized for each injection type using counts and percentages (Table 6.1/6.2). Possible days of maximal ICDRG Score include

the following: Day 4, Day 5, Day 6, Day 7, and Day 14. If the maximal ICDRG Score for an injection type occurred prior to treatment, the subject will be reported as never having had an ICDRG Score more severe than Day 3 for summary purposes.

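### The Regimen 2 48-hour grade-reduction endpoint is zero by construction, and none of the ≥ 1 grade reduction endpoints says which injection type must improve

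*SAP*

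**What the plan says.** Each subject has four patches per regimen, two given rHuPH20 and two given placebo (Protocol 3.1; SAP 3).

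**Responder rule.** All versions require a fall of one grade or more. SAP 8.2 asks, for both regimens, for the share of subjects meeting this, described as "grade reduction of the cutaneous reaction to nickel sulfate in at least one patch region after treatment". For Regimen 2 it adds a second proportion, worded "grade reduction of the cutaneous reaction to nickel sulfate in at least one patch region at 48 hours (Day 3) will be assessed". SAP 2 gives the by-day version as "grade reduction of the cutaneous reaction to nickel sulfate in at least one patch region at Days 4, 5, 6, 7 and 14", where Protocol 2.2 lists Days 2, 3, 4 or 5. SAP 9.1 repeats it as "Proportion of subjects that have a ≥ 1 grade reduction in at least one patch region". None of these names an injection type.

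**Baseline.** SAP 8.4 gives each region its own baseline grade, the Day 3 value, in both regimens.

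**Reporting.** SAP 9.1 states "A qualitative medical review of the ICDRG scores will be used to investigate" the treatment effect and this proportion. It also states "The secondary analysis covers safety and other endpoint parameters (see Section 10"); Section 10 holds only safety analyses. In SAP Appendix A the only ICDRG table is Table 6, day of maximal score.

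**Text pointing to a split by type.** SAP 9.1 says "ICDRG scores will be shown for Treatment Regimen 1 and Treatment Regimen 2 by injection types (rHuPH20 or Placebo) at Baseline" and later days, and describes the primary analysis as a paired within-subject comparison of injections with and without rHuPH20. Protocol 8 says the same of the primary analysis, describes the secondary analysis as a comparison of rHuPH20 with placebo (though it calls the route SC in an intradermal study), and adds "All data collected, including demographics, baseline information, contact dermatitis scoring, safety data, will be summarized by treatment group". Listing 8 and Figure 1 mark every patch A or P.

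**The concern.** These are the trial's only responder endpoints, and the hypotheses are directional: rHuPH20 should lessen the reaction, both as pre-treatment and as treatment (Protocol 8; SAP 9).

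The 48-hour endpoint is the one responder measure aimed at the pre-treatment hypothesis. If its reference value is the measurement itself, it cannot respond to anything.

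For the other endpoints, two analysts could follow SAP 8.2 and obtain different numbers from the same data. One would count any of four patches; the other would count by injection type. The first number does not say which injection did better. If the choice is left until patch identities are known, SAP 4 could lead the by-type version to be classed as post hoc.

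**Working it through.** The sample size of 20 evaluable subjects (SAP 11) has no rate, effect, alpha or power behind it, so there is no planned figure to reproduce. The check concerns the definitions.

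**1. The 48-hour endpoint.** Reduction = baseline grade − grade at the visit. By SAP 8.4 the baseline is the Day 3 grade; by SAP 8.2 the visit is Day 3. For every patch, of either type, the reduction is g(Day 3) − g(Day 3) = 0. The ≥ 1 threshold is never met, so the proportion is 0 of 20 whatever the drug does. No assumption is needed.

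**2. Symmetry of the any-patch rule.** The literal proportion is 1 − P(none of the four patches improves). Injection type does not enter that event, so exchanging the rHuPH20 rate pA and the placebo rate pP changes nothing. The documents give no patch rates; those below are assumed.

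With independent patches:
- any patch: 1 − (1 − pA)²(1 − pP)²
- by type: 1 − (1 − pA)² and 1 − (1 − pP)²

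| pA | pP | Any patch | rHuPH20 | Placebo |
|---|---|---|---|---|
| 0.5 | 0.3 | 1 − 0.25 × 0.49 = 87.8% | 75% | 51% |
| 0.3 | 0.5 | 1 − 0.49 × 0.25 = 87.8% | 51% | 75% |
| 0.3 | 0 | 51% | 51% | 0% |
| 0 | 0.3 | 51% | 0% | 51% |
| 0.163 | 0.163 | 51% | 30% | 30% |

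An any-patch result of 51% therefore fits benefit, harm or no effect.

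Patches on one back at one nickel concentration are probably correlated. Under a probit random-intercept model with rates 0.5 and 0.3, the any-patch proportion is 72.6% at latent correlation 0.5 and 62.1% at 0.8, again the same when the rates are swapped. By type it is 67% against 44%, and 60% against 39%. With fully correlated patches it equals the larger of pA and pP, which is also symmetric.

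**3. How many subjects would count on placebo alone.** Assume no drug effect and a common rate p. Placebo-only responders = P(neither rHuPH20 patch improves) − P(none of four improves). At independence this is (1 − p)² − (1 − p)⁴:
- p = 0.1: 0.81 − 0.6561 = 15%
- p = 0.3: 0.49 − 0.2401 = 25%, or 5.0 of 20 subjects
- p = 0.5: 0.25 − 0.0625 = 19%
- p = 0.8: 0.04 − 0.0016 = 3.8%
- p = 0.9: 0.01 − 0.0001 = 1.0%

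With beta-binomial correlation at p = 0.3 it falls to 0.595 − 0.495 = 10% (2.0 of 20) at ICC 0.5 and 0.658 − 0.621 = 4% (0.7 of 20) at ICC 0.8. These ICCs are on a different scale from the latent correlations in step 2, and the two series should not be compared.

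**4. Precision after a split.** At latent correlation 0.8 in step 2, the expected discordant subjects are 20 × 0.232 = 4.6 (rHuPH20 only) and 20 × 0.018 = 0.4 (placebo only). Purely as a gauge, since no test is planned, a 5-to-0 split has an exact two-sided McNemar p of 2 × 0.5⁵ = 0.0625. The split shows direction, but imprecisely.

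**The case against.** The best answer is that the split was always meant. Protocol 8 describes both the primary and the secondary analysis as rHuPH20 against placebo and summarises scoring by treatment group. SAP 9.1 calls for a paired within-subject comparison and shows scores by type. Only SAP 8.2 read in isolation gives a pooled count. Moreover, no table reports any proportion; the planned outputs are A/P-labelled scores and a medical review of them, and these show direction.

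Most of that stands. A reader might infer that the plan instructs pooling, or that the trial cannot tell whether drug or placebo did better. The documents support neither: no passage instructs pooling, and by-type rates can be derived from Listing 8. A reader might also infer that a split made later must be reported as post hoc. SAP 4 does not settle this, because the by-type display and its medical review are already planned; it could be classed so. Finally, the size in step 3 rests on assumed rates and is small at high rates or high correlation, which cannot be excluded by Day 14.

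What remains is that these passages govern displays and general intent, not who counts as a responder. Where the SAP wants a result per type it says so, as for day of maximal score in SAP 8.1 and Table 6.1.

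None of this answers the Day 3 problem. Protocol 2.2 names no reference for the 48-hour reduction, so another comparator may have been in mind, but SAP 8.4 fixes Day 3 and labelling patches does not help. It would go too far to say that prevention cannot be examined at all: Regimen 2 Day 3 grades are collected and shown by type.

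**Conclusion.** Both parts hold, and they are independent of each other.

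The Regimen 2 48-hour proportion is zero for all subjects under SAP 8.2 and 8.4 taken together, with no assumption required. The remaining ≥ 1 grade endpoints lack the injection type; read literally, the proportion is unchanged when drug and placebo rates are swapped, whatever rates are assumed. Only the illustrative sizes depend on assumed rates and correlations.

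The consequence is limited. The endpoints are secondary and descriptive, no test or sample size depends on them, and the data needed to see direction are collected and listed. What is missing is a definition and a table. This should be fixed, but it does not undermine the design.

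**What to change.** **After-treatment and by-day endpoints (SAP 8.2, 9.1).** Define the responder separately for each injection type within each regimen: a reduction of ≥ 1 grade from the Day 3 grade in at least one of the subject's two patches of that type. Add one descriptive table, for the Evaluable and ITT populations, at the SAP 2 days (4, 5, 6, 7 and 14). It should give both proportions and the paired counts: both types, rHuPH20 only, placebo only, neither. Reconcile those days with the list in Protocol 2.2. Note in the table that about 20 subjects give an imprecise paired difference. For Regimen 2, show the Day 3 grades alongside: a patch graded 0 or 1/2 on Day 3 cannot fall by a whole grade, so successful prevention would leave fewer rHuPH20 patches able to respond.

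**Regimen 2 48-hour endpoint.** Replace change from baseline with a within-subject Day 3 comparison. Take the mean grade of the two patches of each type and report the rHuPH20-minus-placebo difference. Count subjects with rHuPH20 lower by ≥ 1 grade, placebo lower by ≥ 1 grade, or neither, which keeps the protocol's threshold. State how a patch scored as irritant, which has no grade, enters the mean. Align the wording of Protocol 2.2.

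**Cost.** SAP wording, a matching clarification in Protocol 2.2, and one descriptive table. No new data, visits, tests or subjects. Making the change before unblinding avoids any question of post hoc status.
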